9.2.3.2 Adverse Event Overview

An overview of AEs will be presented for the Safety Analysis Set for study Part 1 and Part 2 using SA-P1 and SA-P2, respectively. The overview will consist of the number and percentage of subjects experiencing at least one event for each of the following AE categories:

- Any treatment-emergent AE
- Any treatment-emergent AE related to study drug according to the investigator
- Any severe treatment-emergent AE
- Any serious treatment-emergent AE
- Any treatment-emergent AE leading to discontinuation of study drug
- Any treatment-emergent AE leading to death
- All deaths

9.2.3.3 Treatment-Emergent Adverse Events by SOC and/or PT

Treatment-emergent adverse events will be summarized by SOC and PT for the Safety Analysis Set for study Part 1 and Part 2 using SA-P1 and SA-P2, respectively; by maximum relationship to study drug as assessed by the investigator (e.g., reasonable possibility or no reasonable possibility) and SOC and PT; by maximum severity and SOC and PT; and by subject number and SOC and PT. Specific adverse events will be counted once for each subject for calculating percentages, unless stated otherwise. In addition, if the same adverse event occurs multiple times within a subject, the highest severity and level of relationship to investigational product will be reported.

In addition, treatment-emergent adverse events will be summarized by PT and sorted by decreasing frequency overall.

[figure not shown]
9.2.3.4 SAEs (Including Deaths) and Adverse Events Leading to Study Drug Discontinuation

SAEs (including deaths) and AEs leading to study drug discontinuation will be summarized by SOC and PT and in listing format for the Safety Analysis Set for study Part 1 and Part 2 using SA-P1 and SA-P2, respectively.

9.3 Analysis of Laboratory Data

The clinical laboratory tests defined in the protocol (e.g., hematology and clinical chemistry) will be summarized by regimen for the Safety Analysis Set for study Part 1 and Part 2 using SA-P1 and SA-P2, respectively.

Each laboratory variable will be summarized by visit with the number of non-missing observations, mean and standard deviation, median, minimum and maximum. Mean change from start to end of DB treatment period will be summarized for each laboratory variable by regimen, with the number of observations, mean at start of DB treatment period, and mean at end of DB treatment period. An ANOVA model with treatment as a factor will be used to compare change from start to end of DB treatment period between regimens. The LS mean, standard error, and 95% CI will be presented for the change

from start to end of DB treatment period within each regimen and between regimen difference.

Changes in laboratory parameters during treatment with each regimen will be tabulated using shift tables as low, normal, or high based on the normal ranges of the laboratory used for each sample. A shift table from baseline to any post-baseline value during treatment with each regimen according to the normal range will be provided for each hematology and clinical chemistry parameter.

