Subject will stop DB treatment and will be discharged from the clinical site or designated confinement location, (or begin preparation for DB Treatment Period 2) after the first blue dyed stool following the second dye administration is collected (Visit 3). This could be hospitalization/confinement Day 6, 7 or 8, depending on each subject's gastrointestinal motility.

If subject chooses to leave the clinical site or designated confinement location after DB Treatment Period 1, subject will re-start his/her usual diet and will be given a supply of open label Creon[®] at the dose of open label Creon[®] they received for the screening period to be taken during this period, until returning to the clinical site or designated confinement location, for DB Treatment Period 2. The interval between DB Treatment Period 1 and DB Treatment Period 2 will last up to a maximum of 28 days: In exceptional

circumstances, such as impact by COVID-19-related activities, this period may be extended upon specific consultation with the sponsor. If the subject elects to continue directly into DB Treatment Period 2, and site capacity allows, Visit 4 will be the day following Visit 3.

DB Treatment Period 2 (Visit 4 to Visit 5)

Subject will again be hospitalized/confined (or continue to be hospitalized/confined) at the clinical site or designated confinement location, for approximately 6 to 8 days, starting in the morning (prior to breakfast) of Visit 4 or in the evening (after dinner) on the previous day.

Before any study drug administration on DB Treatment Period 2 Day 1 (Visit 4), subject's weight will be confirmed to be 40 kg or more. Then subjects will stop current open label Creon[®] (if receiving it) and will receive DB study drug and an individualized diet with 100 grams daily fat content, a minimum of 1 g/kg of daily protein and normal to low fiber content for 6 - 8 days. Each subject's diet for the two treatment periods will be created at the same time by a site-based dietitian using ABVDiet, after an interview with the subject, and reviewed and approved by a central dietitian, prior to Visit 2. Dietary surveillance and stool collection will be performed as during DB Treatment Period 1.

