For females of childbearing potential, a serum pregnancy test will be performed at the Screening Visit and a urine pregnancy test will be performed by designated study site personnel at Visit 2 and at Visit 4 (only if subject has not continued confinement from Visit 3), for each study Part.

Females of non-childbearing potential (either postmenopausal or permanently surgically sterile as defined in Section 5.2.4) at Screening do not require pregnancy testing.

Subjects with a positive pregnancy test at the Screening Visit or at Visit 2 or Visit 4 for either study Part may not continue participation in the study and must be discontinued.

Subjects who completed the study Part they were originally enrolled in and agree to participate in the other study Part and it has been ≤ 30 days since Visit 5 of the first Part they participated in will not need to repeat the serum pregnancy test, but will still need to perform the urine pregnancy test as required in Appendix C.

Clinical Laboratory Tests

Samples will be obtained for the laboratory tests listed in Table 1 at the Screening Visit and at Visit 2, Visit 3, Visit, 4 (except if \leq 24 hours post Visit 3) and Visit 5 (ref to Appendix C) for each study Part.

Subjects participating in both Parts and who decide to enter the second study Part directly after the first Part will not need Clinical Laboratory tests done at Visit 1 of the next study Part they are participating in, as long as it has been < 30 days between Visit 5 and Visit 1 of the next study part. The Clinical Laboratory tests done at Visit 5 of the previous study Part will suffice for this requirement at Visit 1 of the next study Part.

Blood draws will be performed after (or at least 30 minutes prior to) vital sign measurements during a visit.

The clinical chemistry should be preferably performed following a fast of a minimum of 8 hours except at the Screening Visit which may be performed in the non-fasting state. Fasting conditions will be reported in the eCRF.

A central laboratory contracted by AbbVie will be utilized for the clinical laboratory tests. Instructions regarding the collection requirements, processing, and shipping of these samples will be provided by the central laboratory.

Hematology	Clinical Chemistry	Urinalysis
Hematocrit	Blood Urea Nitrogen (BUN)	Specific gravity
Hemoglobin	Creatinine	Ketones
Red Blood Cell (RBC) count	Total bilirubin	pH
White Blood Cell (WBC) count	Albumin	Protein

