For each study Part the 2 DB treatment periods will be separated by a maximum of 28 days, unless the subject elects to directly enter DB Treatment Period 2 from DB Treatment Period 1. In exceptional circumstances, such as impact by COVID-19-related activities, this period may be extended upon specific consultation with the sponsor.

At the end of DB Treatment Period 1 (between Visit 3 and Visit 4), the subjects will be given a 30 day supply of open label Creon[®] at the dose they received for the screening period to be taken during this period. In exceptional circumstances, such as impact by COVID-19-related activities, this period may be extended by an additional 30 days upon

specific consultation with the sponsor. If the subject elects to directly enter DB Treatment Period 2, the duration between Visit 3 and Visit 4 will be \leq 24 hours.

During the follow up period for both study parts, subjects will be given, at Visit 5, a supply of open label Creon[®] at the dose they received during the screening period to be taken during this period, along with their usual diet.

The study drug total daily dose, calculated based on the maximum dose of 4,000 LU/g of fat/day, as recommended in the current Creon[®] (Pancrelipase) delayed release capsules 24,000 USP Units (Lipase) label, will be administered orally, divided proportionally based on three meals and two snacks as follows:

Study diet g fat/day	# Capsules/ Meal	# Capsules/ Snack	Total # Capsules/Day	LU/Meal	LU/Snack	Total Daily Dose
100	4	2	16	96,000	48,000	384,000

For each of the treatment periods, the study drug intake will start on Treatment Period Day 1 at breakfast and will continue with each meal/snack until the last stool has been collected. Individual subjects may experience different treatment durations due to the fact the stool collection period depends on their intestinal transit time.

The study drug capsules must be swallowed intact (capsules must not be crushed, chewed or opened), and will be taken during the meal or snack (as per patient's usual practice), with enough fluids to swallow the capsules completely.

All scheduled doses must be taken. Subjects must be encouraged and instructed to consume all food provided as per the individualized diet during hospitalization/confinement.

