8.1.3 Safety Analysis

Safety analyses will be carried out using the Safety Analysis Set. Treatment-emergent AEs and SAEs, will be summarized and reported. Treatment-emergent AEs for DB Treatment Period 1 are defined as reported AEs that have a start date either on or after the first dose of the study drug during DB Treatment Period 1 and up to the end of DB Treatment Period 1. For DB Treatment Period 2, treatment emergent AEs are defined as reported AEs that have a start date either on or after the first dose of study drug during DB Treatment Period 2 and up to the end of DB Treatment Period 2. Adverse Events that occur during the administration of OL Creon[®] will be summarized separately for events that happen during the screening period and after randomization. The number and percent of subjects experiencing AEs will be tabulated by system organ class (SOC) and Medical Dictionary for Drug Regulatory Activities (MedDRA®) preferred term. In addition, summary of AEs by severity and relationship to study drug will be presented. Serious AEs, or AEs that lead to premature study discontinuation will be listed and described in detail. All these summaries will be done by treatment group. Mean change in vital signs and laboratory variables at each visit will be summarized. The last evaluation prior to the first dose of DB study drug in the corresponding treatment period will be used as baseline for the analysis in that treatment period. A frequency table will be presented for Potentially Clinically Important (PCI) vital sign findings. Shift tables for laboratory variables will be presented according to the reference ranges (low, normal or high).

Due to the small number of subjects per treatment group, only summary statistics will be applied to all the safety parameters.

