Appendix C. Study Activities

a. Overall Study Activities for Study Part 1 and Study Part 2

		Double-Blind Treatment Period					Follow-Up Period
	Screening	DB Treatment Period 1		Interval	DB Treatment Period 2		Visit 6
		Visit 2	Visit 3	Un to 28	Visit 4	Visit 5 ^a	30 Days Post Hospital
Activity	Visit 1º	Day 1	Day 6, 7 or 8 ^b	Days ^c	Day 1	Day 6, 7 or 8 ^b	Discharge
Informed Consent ^p	Х						
Medical History	Х	X ^d			X ^f		
Previous dose of PERT	Х				Xf		
Concomitant Medication Review	Х	Х	Х		Х	Х	Х
Physical Examination	X ^r	Х	Х		X ^f	Х	
Height	Х						
Body weight	Х	X ^e	X ^e		X ^e	X ^e	
Vital Signs	X ^r	Х	Х		Х	Х	
Clinical Laboratory Tests	X ^r	Х	Х		X ^f	Х	
Stool Collection for Fecal Elastase Testing	X ^s						
Pregnancy Testing ^g	Х	Х			Х		
Diet Plan Design	X ^h						
Start hospitalization/confinement		Х			X		
IRT system contact	X ⁱ	Xj	X ¹		X ^k	Xq	

			Follow-Up Period				
	Screening	DB Treatment Period 1		Interval	DB Treatment Period 2		Visit 6
		Visit 2	Visit 2 Visit 3		Visit 4 Visit 5 ^a		30 Days Post Hospital
Activity	Visit 1º	Day 1	Day 6, 7 or 8 ^b	Days ^c	Day 1	Day 6, 7 or 8 ^b	Discharge
Adverse Events Review							Х
Study Drug Administration	X						
Treatment Compliance Check							
Diet Administration		See Table b. "	Treatment Periods		See Table b. "T	reatment Periods	
Dietary Records					-	vines .	
Stool Collection							
EPI Symptom Diary							
Hospital/Confinement site discharge			X ^f			X	
COVID-19 Testing		X ^m			X ^{m,n}		
COVID-19 signs and symptoms screening		X			X		

a. Or early termination visit (except hospitalization and stool collection/dietary record).

b. Days 6, 7 or 8 depending on the first appearance of the 2^{nd} dyed stool after the 2^{nd} stool dye marker is administered.

c. In exceptional circumstances, this period may be extended upon consultation with the sponsor.

d. To be updated only if there is new historical information available since Visit 1.

e. Done in the morning prior to any food intake and prior to any blood sampling.

f. If subject elects to enter directly into DB Treatment Period 2 from DB Treatment Period 1, this is not required.

g. For females with child-bearing potential: serum pregnancy test at the Screening Visit (Visit 1) and urine pregnancy test for other visits specified above.

h. Diet plans both the treatment periods for each study Part should be done prior to V2.

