8.4 Secondary Efficacy Endpoint(s) and Analyses

8.4.1 Secondary Efficacy Analyses

[figure not shown]
The secondary efficacy endpoints will be the CNA, stool fat, and stool weight. These variables will also be analyzed separately using a mixed effects model including sequence, period and regimen as fixed effects and subjects within sequence as a random effect. From this model, an estimate of the treatment difference along with a 95% CI will be derived. All comparisons for all secondary variables between the regimen will be descriptive.

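### The between-regimen comparison of laboratory and vital-sign changes uses a treatment-only ANOVA on crossover data, so its standard error and 95% CI are right only if a subject's two changes are uncorrelated.

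*SAP*

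**What the plan says.** SAP section 9.3 (laboratory data) specifies: "An ANOVA model with treatment as a factor will be used to compare change from start to end of DB treatment period between regimens". Section 9.4 (vital signs) uses the same sentence. Both sections then promise the LS mean, standard error and 95% CI for the change within each regimen and for the difference between regimens. Treatment is the only model term named.

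For the same two-period, two-sequence design, the SAP analyses CFA (section 8.3.1) and the secondary endpoints (section 8.4.1) "using a mixed effects model including sequence, period and regimen as fixed effects and subjects within sequence as a random effect".

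Protocol section 8.1.3 says that, because groups are small, "only summary statistics will be applied to all the safety parameters". It also defines the baseline for each period: "The last evaluation prior to the first dose of DB study drug in the corresponding treatment period will be used as baseline".

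On the schedule, protocol section 5.3.1.1 drops the Visit 4 laboratory draw when it would fall within 24 hours of Visit 3. Appendix C attaches footnote f to that draw: "If subject elects to enter directly into DB Treatment Period 2 from DB Treatment Period 1, this is not required". Going straight on is the subject's choice (protocol section 5.1: "If the subject elects to continue directly into DB Treatment Period 2, and site capacity allows"). Section 5.5.1 puts the gap between Visits 3 and 4 at no more than 24 hours in that case. Vital signs and body weight keep their own Visit 4 measurement.

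**The concern.** A one-factor ANOVA treats the changes under the two regimens as if they came from separate subjects. Here nearly every subject in the Safety Analysis Set contributes to both. The difference between regimens is therefore a within-subject contrast, and its variance depends on how a subject's two changes correlate. A model without a subject term or within-subject covariance cannot reflect that.

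Omitting period has two further effects. Any period effect stays in the residual, and part of it enters the estimated difference if the sequences are unequal in size.

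At stake is an interval that a reader would use to judge whether each new product resembles Creon on laboratory values and vital signs, which SAP section 3.4 lists as safety variables. The within-regimen intervals, adverse event tables, shift tables, counts of potentially clinically important values and the CFA test do not depend on this model.

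**Working it through.** **Inputs.** The planned completers are 22 in Part 1 and 18 in Part 2 (protocol section 8.2.2, SAP section 2.4). The model terms are those quoted above. Neither rho nor the share of subjects who go straight into Period 2 is given, so both are varied as assumptions. The plan states no standard error or CI width for these analyses, so there is no figure to reproduce.

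**Standard error.** With N complete pairs and equal variance s² for each change:

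- true variance of the difference: 2s²(1 - rho)/N
- variance estimated by treatment-only ANOVA: 2s²/N, with 2N - 2 df
- estimated SE / true SE = 1/sqrt(1 - rho)

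**Coverage.** These are results from 40,000 simulated crossovers per case, with normal errors, equal sequences and no period effect:

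| rho | SE ratio | Coverage, N = 18 | Coverage, N = 22 |
|---|---|---|---|
| -0.50 | 0.82 | 88.9% | 89.0% |
| -0.25 | 0.89 | 92.2% | 92.3% |
| 0 | 1.00 | 94.9% | 95.0% |
| +0.25 | 1.15 | 97.6% | 97.5% |
| +0.50 | 1.41 | 99.2% | 99.3% |

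A model with sequence, period, regimen and an unrestricted within-subject covariance covers 94.8% to 95.3% in every case. Within-regimen coverage stays at 94.7% to 95.2%.

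**Why rho is likely negative for laboratory values.** Write V2, V3 and V5 for the values at those visits. A subject who goes straight on has change 1 = V3 - V2 and change 2 = V5 - V3. With independent visit errors of equal variance v, the covariance is -v and each change has variance 2v, so rho = -v/(2v) = -0.5. Other subjects have a separate V4, and under the same assumption their rho is 0. By share of subjects going straight on:

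| Share | Coverage, N = 18 | Coverage, N = 22 |
|---|---|---|
| 0% | 94.8% | 95.0% |
| 25% | 93.6% | 93.5% |
| 50% | 91.9% | 92.0% |
| 75% | 90.6% | 90.8% |
| 100% | 89.1% | 89.0% |

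**Period effect.** Bias in the estimated difference = (nB - nA)/N × period effect, where nA and nB are the two sequence sizes. As illustrations, a 10 v 8 split passes on 2/18 = 11% of the period effect, and a 13 v 9 split passes on 4/22 = 18%. With equal sequences there is no bias. However, a period effect of 1 SD at rho = 0 and N = 20 inflates the SE by 13% (coverage 97.2%).

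**Change in interval width.** Correct width / planned width = sqrt(1 - rho) × t(N-2)/t(2N-2). For N = 18 / 22 this is 1.28 / 1.27 at rho = -0.5, 1.04 / 1.03 at 0 and 0.74 / 0.73 at +0.5.

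**The case against.** The best counter-argument is that little hangs on this. Safety is judged from descriptive tables, no rule uses the intervals, and with complete, balanced sequences the point estimate is unbiased. That is true, and it limits the importance of the point. It does not make the interval correct.

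Next, the size is not established. The 89% figure needs every subject to go straight on, and independent visit errors. If a subject's deviations persist between visits, with an assumed lag-one correlation r, the shared Visit 3 value gives rho = -(1 - r)/2. With all subjects going straight on and N = 20, coverage is then 89.1%, 92.3% and 93.8% at r = 0, 0.5 and 0.8. With half going straight on, it is 92.1%, 92.7% and 94.0%. This stands as a limit on size. Under this model rho remains negative, so the direction for laboratory values holds. A subject-specific response to the study diet could push rho upwards in those who go home between periods, and the documents cannot rule that out.

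For vital signs, a Visit 4 reading one day after Visit 3 could nearly repeat it and produce some negative correlation. That is possible, but it is not the shared-value mechanism, and the documents do not settle the sign.

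Finally, protocol section 8.1 delegates analysis details to the SAP. That permits the SAP to add detail, but it does not reconcile a between-regimen model with a protocol statement limiting safety to summary statistics.

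**Conclusion.** The concern holds. As written, the between-regimen standard error and 95% CI in SAP sections 9.3 and 9.4 are valid only if rho is 0 and there is no period effect, apart from a chance offset between the two. The omission is clear from the text; its size is conditional. Over the assumed range of rho from -0.5 to +0.5, coverage runs from about 89% to 99%. For laboratory values the likely direction is too narrow, to an extent set by the share of subjects who go straight into Period 2 and by how far deviations persist between visits. For vital signs the direction is open. The figures assume complete pairs, equal variances and normal errors. The SAP should be corrected, but neither the non-inferiority conclusion nor any other decision rule is affected.

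**What to change.** In SAP sections 9.3 and 9.4, take the between-regimen difference from a model with sequence, period and regimen as fixed effects. Use a within-subject covariance that can be negative (unstructured, or compound symmetry without a lower bound), and keep subjects dosed in one period only. Paired within-subject differences adjusted for sequence also allow either sign of rho, but they use completers only. If this model is kept, protocol section 8.1.3 needs reconciling with it.

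The alternative is to delete the between-regimen standard error and CI, which brings the SAP into line with protocol section 8.1.3. The within-regimen summaries can stay under either option.

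The CFA model statement should not simply be copied. If its random subject variance is bounded at zero, coverage at rho = -0.5 stays at 89.0% to 89.3% with pooled df, or 90.2% to 90.4% with N - 2 df. The SAP does not say whether that bound applies.

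The cost is SAP wording and a small programming change. Intervals would widen by about 27% at rho = -0.5 and by 3 to 4% at rho = 0 (fewer df), and would narrow by about 26% at rho = +0.5.

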9.4 Analysis of Vital Signs

[figure not shown]
Vital sign measurements of systolic and diastolic blood pressure, pulse rate, weight, and body temperature will be summarized by regimen for the Safety Analysis Set for study Part 1 and Part 2 using SA-P1 and SA-P2, respectively.

Each vital sign variable will be summarized by visit with the number of non-missing observations, mean and standard deviation, median, minimum and maximum. Mean change from start to end of DB treatment period will be summarized for each vital sign variable by regimen, with the number of observations, mean at start of DB treatment period, and mean at end of DB treatment period. An ANOVA model with treatment as a factor will be used to compare change from start to end of DB treatment period between regimens. The LS mean, standard error, and 95% CI will be presented for the change from start to end of DB treatment period within each regimen and between regimen difference.

Vital sign variables will be evaluated based on potentially clinically important (PCI) criteria (Appendix B). For each vital sign PCI criterion, the number and percentage of subjects who have a vital sign value meeting the criteria will be summarized by regimen.

